4.2. Eligibility Criteria

4.2.1. Inclusion Criteria

A patient will be eligible for inclusion in this study only if ALL of the following criteria apply:

- Men or women age 18 - 75 years;
- Patient with a confirmed and documented diagnosis of adult-onset rheumatoid arthritis, for at least 12 weeks, according to the revised 2010 ACR-EULAR classification criteria, including at least one positive criteria among the following: Rheumatoid Factor (RF), Anti-Citrullinated Peptide Antibody (ACPA) or bone erosion;
- Swollen joint count of ≥ 4 (28-joint count) and tender joint count ≥ 4 (28-joint count) at screening;
- Patient with a moderate to severe disease activity score DAS28 CRP of ≥ 3.2 and CRP ≥ 5 mg/L (≥ 4.76 nmol/L) at screening;
- Patient who had an inadequate response (IR), or failed either methotrexate (MTX) or/and anti-TNF α therapy (both administered for at least 12 weeks before IR) or were intolerant to anti-TNF α therapy.

In addition, MTX treatment should be given at a stable dose ≥ 10 mg/week (for at least 4 weeks prior to randomization). The maximal dose of methotrexate should not exceed a total of 20 mg/week. MTX treatment should be associated with folic acid at a dose ≥ 5 mg/week.

For the anti-TNF α therapy, the following wash-out period will be required:

- 30 days prior to randomization for adalimumab and etanercept
- 2 months prior to randomization for infliximab, certolizumab pegol, golimumab
- Patients with the following hematological and biochemical laboratory parameters obtained within 14 days prior to baseline:
 - Hemoglobin > 9.0 g dL $^{-1}$;
 - Absolute neutrophil count ≥ 1000 mm $^{-3}$;
 - Platelets $\geq 100,000$ mm $^{-3}$;
 - Total serum creatinine ≤ 1.3 x ULN (upper limit of normal);
 - Creatinine clearance > 50 mL min $^{-1}$ by the Cockcroft-Gault equation within 60 days prior to baseline;
 - Total serum bilirubin < 1.5 x ULN;
 - Alkaline phosphatase, AST (SGOT) and ALT (SGPT) < 1.5 x ULN;
 - Negative screening for TB and HIV, HCV, HBV
- Patients are able and willing to comply with study visits and procedures as per protocol;
- Patients should understand, sign and date the written voluntary informed consent form at the screening visit prior to any protocol-specific procedures are performed;
- Patients should be affiliated to a social security regimen (for French sites only);

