4.2 Posology and method of administration

Metoject should only be prescribed by physicians who are familiar with the various characteristics of the medicinal product and its mode of action. The administration should routinely be done by health professionals. If the clinical situation permits the treating physician can, in selected cases, delegate the subcutaneous administration to the patient her/himself. In these cases, detailed administration instructions from the physician are obligate. Metoject is injected **once weekly**.

The patient is to be explicitly informed about the fact of administration **once weekly**. It is advisable to determine a fixed, appropriate weekday as day of injection.

Methotrexate elimination is reduced in patients with a third distribution space (ascites, pleural effusions).

Such patients require especially careful monitoring for toxicity, and require dose reduction or, in some cases, discontinuation of methotrexate administration (see section 5.2 and 4.4).

Dosage in adult patients with rheumatoid arthritis

The recommended initial dose is 7.5 mg of methotrexate **once weekly**, administered either

subcutaneously, intramuscularly or intravenously. Depending on the individual activity of the disease and tolerability by the patient, the initial dose may be increased gradually by 2.5 mg per week. A weekly dose of 25 mg should in general not be exceeded. However, doses exceeding 20 mg/week are associated with significant increase in toxicity, especially bone marrow suppression. Response to treatment can be expected after approximately 4 – 8 weeks. Upon achieving the therapeutically desired result, the dose should be reduced gradually to the lowest possible effective maintenance dose.

Dosage in children and adolescents below 16 years with polyarthritic forms of juvenile idiopathic arthritis

The recommended dose is 10 – 15 mg/m² body surface area (BSA)/**once weekly**. In therapy-refractory cases the weekly dosage may be increased up to 20 mg/m² body surface area/**once weekly**. However, an increased monitoring frequency is indicated if the dose is increased.

Due to limited data availability about intravenous use in children and adolescents, parenteral administration is limited to subcutaneous and intramuscular injection.

Patients with JIA should always be referred to a rheumatology specialist in the treatment of children/adolescents.

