Use in children < 3 years of age is not recommended as insufficient data on efficacy and safety is available for this population (see section 4.4).

Dosage in patients with psoriasis vulgaris and psoriatic arthritis

It is recommended that a test dose of 5 – 10 mg should be administered parenterally, one week prior to therapy to detect idiosyncratic adverse reactions. The recommended initial dose is 7.5 mg of methotrexate **once weekly**, administered either subcutaneously, intramuscularly or intravenously. The dose is to be increased gradually but should not, in general, exceed a weekly dose of 25 mg of methotrexate. Doses exceeding 20 mg per week can be associated with significant increase in toxicity, especially bone marrow suppression. Response to treatment can generally be expected after approximately 2 – 6 weeks. Upon achieving the therapeutically desired result, the dose should be reduced gradually to the lowest possible effective maintenance dose.

Dosage in patients with Crohn's disease

• Induction treatment:

25 mg/week administered either subcutaneously, intravenously or intramuscularly.

Response to treatment can be expected after approximately 8 to 12 weeks.

• Maintenance treatment:

15 mg/week administered either subcutaneously, intravenously or intramuscularly.

There is not sufficient experience in the paediatric population to recommend Metoject for the treatment of Crohn's disease in this population.

Maximum weekly dose

The dose should be increased as necessary but should in general not exceed the maximum recommended weekly dose of 25 mg. In a few exceptional cases a higher dose might be clinically justified, but should not exceed a maximum weekly dose of 30 mg of methotrexate as toxicity will markedly increase.

Patients with renal impairment

Metoject should be used with caution in patients with impaired renal function. The dose should be adjusted as follows:

Creatinine clearance (ml/min)	Dose
≥ 60	100 %
30 – 59	50 %
< 30	Metoject must not be used

See section 4.3.

Patients with hepatic impairment

Methotrexate should be administered with great caution, if at all, to patients with significant current or previous liver disease, especially if due to alcohol. If bilirubin is > 5 mg/dl (85.5 μ mol/l), methotrexate is contraindicated.

For the full list of contraindications, see section 4.3.

Use in elderly patients

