Dose reduction should be considered in elderly patients due to reduced liver and kidney function as well as lower folate reserves which occur with increased age.

Use in patient with a third distribution space (pleural effusions, ascitis)

As the half-life of methotrexate can be prolonged to 4 times the normal length in patients who possess a third distribution space dose reduction or, in some cases, discontinuation of methotrexate administration may be required (see section 5.2 and 4.4).

Method of administration

The medicinal product is for single use only.

Metoject can be given by intramuscular, intravenous or subcutaneous route (in children and adolescents only subcutaneous or intramuscular).

The overall duration of the treatment is decided by the physician.

Note:

If changing the oral application to parenteral administration a reduction of the dose may be required due to the variable bioavailability of methotrexate after oral administration.

Folic acid supplementation may be considered according to current treatment guidelines.

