4.3 Contraindications

Metoject is contraindicated in the case of

- hypersensitivity to the active substance or to any of the excipients listed in section 6.1,
- severe liver impairment (see section 4.2),
- alcohol abuse,
- severe renal impairment (creatinine clearance less than 30 ml/min., see section 4.2 and section 4.4),
- pre-existing blood dyscrasias, such as bone marrow hypoplasia, leukopenia, thrombocytopenia, or significant anaemia,
- serious, acute or chronic infections such as tuberculosis, HIV or other immunodeficiency syndromes,
- ulcers of the oral cavity and known active gastrointestinal ulcer disease,
- pregnancy and breast-feeding (see section 4.6),
- concurrent vaccination with live vaccines.

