For psoriasis patients the need of a liver biopsy prior to and during therapy is controversial. Further research is needed to establish whether serial liver chemistry tests or propeptide of type III collagen can detect hepatotoxicity sufficiently. The evaluation should be performed case by case and differentiate between patients with no risk factors and patients with risk factors such as excessive prior alcohol consumption, persistent elevation of liver enzymes, history of liver disease, family history of inheritable liver disease, diabetes mellitus, obesity, and history of significant exposure to hepatotoxic drugs or chemicals and prolonged methotrexate treatment or cumulative doses of 1.5 g or more.
Check of liver-related enzymes in serum: Temporary increases in transaminases to twice or three times of the upper limit of normal have been reported by patients at a frequency of 13 – 20 %. In the case of a constant increase in liver-related enzymes, a reduction of the dose or discontinuation of therapy should be taken into consideration.
Due to its potentially toxic effect on the liver, additional hepatotoxic medicinal products should not be taken during treatment with methotrexate *unless clearly necessary* and the consumption of alcohol should be avoided or greatly reduced (see section 4.5). Closer monitoring of liver enzymes should be exercised in patients taking other hepatotoxic medicinal products concomitantly (e.g. leflunomide).
The same should be taken into account with the simultaneous administration of haematotoxic medicinal products (e.g. leflunomide).
4. Renal function should be monitored by renal function tests and urinalysis (see sections 4.2 and 4.3).
As methotrexate is eliminated mainly by renal route, increased serum concentrations are to be expected in the case of renal impairment, which may result in severe undesirable effects. Where renal function may be compromised (e.g. in the elderly), monitoring should take place more frequently. This applies in particular when medicinal products are administered concomitantly that affect the elimination of methotrexate, cause kidney damage (e.g. non-steroidal anti-inflammatory medicinal products) or that can potentially lead to impairment of blood formation. Dehydration may also intensify the toxicity of methotrexate.

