5.2 Pharmacokinetic properties

Absorption

Following oral administration, methotrexate is absorbed from the gastrointestinal tract. In case of low-dosed administration (dosages between 7.5 mg/m² and 80 mg/m² body surface area), the mean bioavailability is approx. 70 %, but considerable interindividual and intraindividual deviations are possible (25 – 100 %). Maximum serum concentrations are achieved after 1 – 2 hours.

Bioavailability of subcutaneous, intravenous and intramuscular injection is comparable and nearly 100%.

Distribution

Approximately 50 % of methotrexate is bound to serum proteins. Upon being distributed into body tissues, high concentrations in the form of polyglutamates are found in the liver, kidneys and spleen in particular, which can be retained for weeks or months. When administered in small doses, methotrexate passes into the cerebrospinal fluid in minimal amounts. The terminal half-life is on average 6 – 7 hours and demonstrates considerable variation (3 – 17 hours). The half-life can be prolonged to 4 times the normal length in patients who possess a third distribution space (pleural effusion, ascites).

Biotransformation

Approx. 10 % of the administered methotrexate dose is metabolised intrahepatically. The principle metabolite is 7-hydroxymethotrexate.

Elimination

Excretion takes places, mainly in unchanged form, primarily renal via glomerular filtration and active secretion in the proximal tubulus.

Approx. 5 – 20 % methotrexate and 1 – 5 % 7-hydroxymethotrexate are eliminated biliary. There is pronounced enterohepatic circulation.

In the case of renal impairment, elimination is delayed significantly. Impaired elimination with regard to hepatic impairment is not known.

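### Methotrexate has no renal exception: creatinine clearance of 50 to 60 mL/min is admitted on up to 20 mg/week, where the label in Appendix 5 gives half the dose

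*Protocol*

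**What the plan says.** **Entry.** Protocol 4.2.1, the synopsis and SAP 3.2.1 require "Creatinine clearance > 50 mL min" by Cockcroft-Gault within 60 days before baseline, and serum creatinine up to 1.3 × ULN. MTX must have been stable for at least 4 weeks at 10 mg/week or more, with a ceiling of 20 mg/week. No line links the MTX dose to clearance.

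**On study.** Protocol 5.12.1, the synopsis (Medications), SAP 3.3 and SAP 11.8 keep MTX at 10 mg/week or more and unchanged to the end. None has a renal exception. Section 6.2 gives liver thresholds for stopping study treatment but no renal threshold and no step for MTX.

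**The attached label.** Appendix 5 is the label of an injectable MTX product. Its section 4.2 says "Metoject should be used with caution in patients with impaired renal function. The dose should be adjusted as follows": 100% at 60 mL/min or more, 50% at 30–59, and no use below 30. Its section 4.3 lists "severe renal impairment (creatinine clearance less than 30 ml/min., see section 4.2 and section 4.4" among the contraindications. Sections 5.12.1 and the synopsis refer to Appendix 5 only for drug interactions.

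**The concern.** Both texts sit in one document and give different answers for the same patient. At a clearance of 55 mL/min, the body of the protocol accepts an unreduced 20 mg/week and asks that it not change, whereas the attached label asks for half. Label section 4.4 states why this matters: "increased serum concentrations are to be expected in the case of renal impairment, which may result in severe undesirable effects".

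Some features of the trial make the situation plausible. Patients up to 75 years may enter, and the label advises considering dose reduction in the elderly. Stable NSAIDs are allowed, and the label asks for more frequent renal monitoring with them where renal function may be compromised. The qualifying clearance may be up to 60 days old, while the other laboratory criteria allow 14 days.

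The second half of the concern is a fall in clearance during the 12 weeks. Creatinine is measured at every visit, so the fall would be seen, but the plan does not say that MTX may be reduced while the patient continues.

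**Working it through.** **Inputs.** Clearance limit, MTX floor (10 mg/week) and ceiling (20 mg/week): protocol 4.2.1 and 5.12.1. Label share of dose (50% at 30–59 mL/min): Appendix 5, label 4.2. Oral bioavailability: label 5.2. Planned size (60): protocol 4.1.

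**1. The band.** The protocol admits clearance above 50; the label gives the full dose only from 60. The overlap in conflict at entry is above 50 and below 60 mL/min.

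**2. Half of each permitted dose, against the 10 mg floor (0.5 × dose).**

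| MTX, mg/week | Half | At or above 10? |
|---|---|---|
| 10 | 5 | no |
| 12.5 | 6.25 | no |
| 15 | 7.5 | no |
| 17.5 | 8.75 | no |
| 20 | 10 | yes |

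Only 20 mg/week halves to a permitted dose, and making that change on study still departs from the stable-dose rule.

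**3. Does the serum creatinine limit close the band?** Take an assumed woman of 70 years and 60 kg. Standard Cockcroft-Gault gives (140 − 70) × 60 × 0.85 / (72 × Scr) = 49.6/Scr. At 0.9 mg/dL this is 55 mL/min. With an assumed ULN of 0.9 to 1.1 mg/dL, 1.3 × ULN is 1.17 to 1.43 mg/dL, so she passes. The limit does not close the band.

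**4. How far does the answer depend on how the 50% is read?** The label prints no mg limit for the band. Three readings are possible.

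- Half of the usual maximum ("A weekly dose of 25 mg should in general not be exceeded"): 25 × 0.5 = 12.5 mg/week.
- Half of the exceptional maximum ("should not exceed a maximum weekly dose of 30 mg of methotrexate"): 30 × 0.5 = 15 mg/week.
- Half of the patient's own full dose: an unreduced 10 mg/week also departs, and a dose already halved does not.

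**5. Route.** The protocol does not state the MTX route. For oral use, label 5.2 says "the mean bioavailability is approx. 70 %, but considerable interindividual and intraindividual deviations are possible" (25–100%). At 70%, the oral equivalents of the two derived lines are 12.5/0.70 = 17.9 and 15/0.70 = 21.4 mg/week. The second is above the 20 mg ceiling. On mean exposure, the oral conflict is therefore limited to doses above 17.9 mg/week on the first reading, and disappears on the second. The label's own caution about switching route points the same way: "If changing the oral application to parenteral administration a reduction of the dose may be required".

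**6. Numbers.** The documents give no distribution of clearance. If 1%, 5% or 10% of 60 patients are in the band (assumption), that is 0.6, 3 or 6 patients, before allowing for dose, route and prior adjustment.

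**The case against.** The strongest reply is that nothing in the trial's rules is breached. Appendix 5 is the label of one injectable product, attached for interactions. MTX is background therapy that the protocol neither starts nor raises, and the 20 mg ceiling is the level above which the label itself warns of significantly more toxicity. Investigators can exclude a patient for clinically relevant renal abnormality or for any condition that threatens safety (4.2.2), and can withdraw a patient at any time (6.2). A patient already adjusted to 10 mg/week or more satisfies both texts. All of this stands and limits the point's weight. It does not remove the point, because the safeguards are discretionary and none ties the MTX dose to clearance.

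Two stronger readings are tempting.

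- A reader might infer a fixed cap of 12.5 mg/week in the band. The documents do not support one: the label prints only a percentage, the 12.5 and 15 mg lines are derived, and such a cap would exclude some oral patients whose mean exposure lies below it.
- A reader might infer that a site cannot reduce MTX and continue. The documents do not say so. Section 8.1.1 requires discontinuation only for major deviations, which are classed at the blind-review meeting. Its listed item concerns study treatment, which section 5.4 describes as the ABX464 or placebo capsules; SAP 5.1 defines study drug in the same way. On the other side, SAP 3.3 lists MTX under its study-treatment heading, and the list in 8.1.1 is not exhaustive. The status of such a reduction is unclear, not settled.

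**Conclusion.** The mismatch is real. Followed as written, the entry and stable-dose rules can keep a patient on more MTX than the attached label supports at that clearance, and no text expressly provides for a label-consistent reduction on study. It is a minor patient-safety and consistency point, and a cheap improvement.

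Its size is uncertain. It rests on an assumed share of patients in the band, on the unstated MTX route, and on how the label's 50% is read. After these limits the number affected may be none. All three arms take MTX, so no treatment comparison, power or error rate changes. The most direct consequence for the analysis is that a patient withdrawn for this reason is not replaced (6.2).

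It would go too far to infer that the protocol violates its own MTX dosing rule: it contains no renal dosing rule, and Appendix 5 is not adopted as one.

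**What to change.** Keep the limit above 50 mL/min and add two sentences.

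1. In 4.2.1, the synopsis criteria and SAP 3.2.1: *If creatinine clearance is < 60 mL/min, the stable MTX dose must already have been adjusted for renal function according to its label.* No fixed mg cap.
2. In 5.12.1, the synopsis Medications, SAP 3.3 and SAP 11.8: *Exception: MTX may be reduced, including below 10 mg/week, for a fall in renal function according to its label; the change is recorded in the eCRF and does not by itself require discontinuation. If clearance falls below 30 mL/min, MTX is stopped and the patient is withdrawn from study treatment.*

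Per Protocol status after a reduction should be decided at the blind-review meeting and not granted automatically: the trial tests ABX464 combined with MTX, and a cut in MTX could plausibly affect ACR20. Withdrawal below 30 mL/min follows for the same reason, since the combination under test no longer exists.

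Raising the entry limit to 60 mL/min would close the entry gap but leave a fall in clearance on study uncovered.

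**Cost.** Seven places in the text change. A few candidates may be lost: if the 50% is taken of the patient's own dose, only those with a full dose of at least 10/0.5 = 20 mg/week still meet the 10 mg entry floor after adjustment. Clearance has to be calculated at each visit, a new task, but from creatinine and weight already collected. Background MTX will change in a few patients.

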4.2.2. Exclusion Criteria

The following criteria should be checked at the time of screening. If ANY exclusion criterion applies, the patient will not be included in the study:

- Patient with a known positive anti-double stranded deoxyribonucleic acid (DNA [anti-dsDNA]) and confirmed diagnosis of systemic lupus erythematosus (SLE);
- Patients with active infection or the following history of infection(s) (the list is not exhaustive):
 - Active infection (except benign infections, according to investigator's opinion) within 14 days prior to inclusion.
 - Serious infection, defined as an infection requiring hospitalization or IV infusion of anti-infective agents in the 2 months prior to inclusion.
 - A history of opportunistic, recurrent or chronic infections that, in the investigator's opinion, could render this study detrimental to the patient.
- Patients who have received or are expected to receive a live (including attenuated) vaccine within 3 months prior to baseline;
- Acute, chronic or history of clinically relevant (as per investigator's judgement) pulmonary, cardiovascular, hepatic, pancreatic or renal functional abnormality, encephalopathy, neuropathy or unstable CNS pathology such as seizure disorder, angina or cardiac arrhythmias, active malignancy or any other clinically significant medical problems as determined by physical examination and/or laboratory screening tests and/or medical history;
- Acute, chronic or history of immunodeficiency or other autoimmune disease;
- Patient previously treated with any (approved or investigational) non-anti-TNF biological disease-modifying antirheumatic drugs (bDMARDs), and targeted DMARDs (tDMARDs) prior to baseline. These treatments include: IL-6 antagonists, Janus Kinase (JAK) inhibitors, cytotoxic T lymphocyte-associated molecule CTLA-4Fc Chimera, rituximab;
- Patient treated with systemic corticosteroids >10 mg/day during the 2 weeks prior to and at randomization; IV or IM injections of glucocorticoids 4 weeks prior to randomization and IA glucocorticoids 2 weeks prior to randomization;
- Patients treated with other immunosuppressive drugs;
- History of malignancy (other than resected cutaneous basal cell or squamous cell carcinoma that has been treated with no evidence of recurrence) unless it has been treated and a cure is achieved for at least 5 years;
- Serious illness requiring systemic treatment and/or hospitalization within 3 weeks prior to baseline;
- Pregnant or breast-feeding woman;
- Illicit drug or alcohol abuse or dependency;
- Use of any investigational or non-registered product within 3 months or within 5 half-lives preceding baseline, whichever is longer;
- Any condition, which in the opinion of the investigator, could compromise the patient's safety or adherence to the study protocol.

